9.5. Subgroup Efficacy Analyses (Dupilumab Naïve and Patients Previously Exposed to Dupilumab)

The same analyses described for the Primary efficacy analyses (Section 9.3) will be performed by previous exposure to dupilumab (Yes/No), for CCI purposes.

All efficacy variables for the Maintenance Period for subgroup analyses will be analysed by means of descriptive statistics presented by treatment group as randomised during the Induction Period, in the same way as for the primary and secondary efficacy analyses on the overall population.

9.6. Summary of the Statistical Efficacy Analysis to be performed with Induction period data

This document is confidential.

The table below provides the detailed analyses relative to estimands including analysis type, method and imputation, population, time point, and treatment comparisons for efficacy/health outcomes analyses.

Measure	Variable	Estimand (Section 6)	Analysis Method (Section 6.3)	Population (Section 5)	Analysis Type
Eczema Area and Severity Index (EASI)	Proportion of patients achieving EASI 75 at W16	Primary Estimand (Hybrid)	CMH analysis with MCMC-MI	FAS PPS	Primary analysis: EASI 75 at W16 Key secondary analysis: EASI 90 at W16 EASI 75; 90 and 50 up to W16
		Supportive Estimand (Hypothetical)	NRI	FAS	Primary analysis: EASI 75 at W16 Key secondary analysis: EASI 90 at W16 EASI 75; 90 and 50 up to W16
	Time to EASI 75	NA	NA	FAS	CCI analysis: time to EASI 50-75-90 up to W16
Investigator's Global Assessment (IGA)	Proportion of patients achieving IGA [0,1] with a ≥ 2 -point improvement at W16	Primary Estimand (Hybrid)	MCMC-MI	FAS PPS	Key secondary analysis: achieving IGA [0,1] with a ≥ 2 -point improvement at W16

This document is confidential.

Measure	Variable	Estimand (Section 6)	Analysis Method (Section 6.3)	Population (Section 5)	Analysis Type
		Supportive Estimand (Hypothetical)	NRI	FAS	Key secondary analysis: achieving IGA [0,1] with a ≥2-point improvement at W16
Pruritus NRS	Proportion of patients achieving at least 4-point improvement in pruritus NRS at W16	Primary Estimand (Hybrid)	MCMC-MI	FAS* PPS*	Key secondary analysis: achieving at least 4-point improvement in pruritus NRS at W16
		Supportive Estimand (Hypothetical)	NRI	FAS*	Key secondary analysis: achieving at least 4-point improvement in pruritus NRS at W16
	Change from baseline in Pruritus NRS up to W16	Primary Estimand (Hybrid)	MMRM and BOCF	FAS	Key secondary analysis: Change from baseline in Pruritus NRS up to W16
Body Surface Area (BSA)	Change from baseline in BSA score up to W16	Primary Estimand (Hybrid)	MMRM and BOCF	FAS	Key secondary analysis: Change from baseline in BSA score up to W16

This document is confidential.

Measure	Variable	Estimand (Section 6)	Analysis Method (Section 6.3)	Population (Section 5)	Analysis Type
SCORing Atopic Dermatitis (SCORAD)	Change from baseline in SCORAD score up to W16	Primary Estimand (Hybrid)	MMRM and BOCF	FAS	Key secondary analysis: Change from baseline in SCORAD score up to W16
Sleep-loss Score	Change from baseline sleep loss up to W16	Primary Estimand (Hybrid)	MMRM and BOCF	FAS	Key secondary analysis: Change from baseline sleep loss up to W16
Patient-Oriented Eczema Measure (POEM)	Change from baseline in POEM score	Primary Estimand (Hybrid)	MMRM and BOCF	FAS	Key secondary analysis: Change from baseline POEM up to W16
(Children) Dermatology Life Quality Index (DLQI/ CDLQI)	Change from baseline in DLQI total score up to W16	Primary Estimand (Hybrid)	MMRM and BOCF	FAS	Key secondary analysis: Change from baseline DLQI/ CDLQI up to W16
	Change from baseline in CDLQI total score up to W16	Primary Estimand (Hybrid)	MMRM and BOCF	FAS*	Key secondary analysis: achieving at least 4-point improvement in DLQI up to W16
	Proportion of patients achieving at least 4-point improvement in DLQI up to W16	Primary Estimand (Hybrid)	MMRM and BOCF	FAS*	Key secondary analysis: achieving at least 4-point improvement in DLQI up to W16

This document is confidential.

Measure	Variable	Estimand (Section 6)	Analysis Method (Section 6.3)	Population (Section 5)	Analysis Type
Topical corticosteroids (TCS)-free TCS data collected in CRF and not from eDiary.	Proportion of TCS-free days up to W16	Primary Estimand (Hybrid)	MMRM and BOCF	FAS	Key secondary analysis: Proportion of TCS-free days up to W16
	Time to TCS-free days up to W16	Primary Estimand (Hybrid)	Kaplan-Meier	FAS	Key secondary analysis: Time to TCS-free days up to W16
	Time to TCS-free days up to W16	Secondary Estimand (Composite)	Kaplan-Meier	FAS	Key secondary analysis: Time to TCS-free days up to W16
Skin Pain NRS	Change from baseline Skin Pain NRS up to W16	Primary Estimand (Hybrid)	MMRM and BOCF	FAS	Key secondary analysis: Change from baseline Skin Pain NRS up to W16
	Percentage of patients achieving a 4-point improvement Skin Pain NRS at W16	Primary Estimand (Hybrid)	MMRM and BOCF	FAS*	Key secondary analysis: Percentage of patients achieving a 4-point improvement Skin Pain NRS at W16
Recap of atopic eczema (RECAP)	Change from Baseline RECAP up to W16	Primary Estimand (Hybrid)	MMRM and BOCF	FAS	CCI [REDACTED] analysis: Change from Baseline RECAP up to W16

This document is confidential.

Measure	Variable	Estimand (Section 6)	Analysis Method (Section 6.3)	Population (Section 5)	Analysis Type
World Health Organisation – Five Well-Being Index (WHO-5)	Change from Baseline WHO-5 up to W16	Primary Estimand (Hybrid)	MMRM and BOCF	FAS	CCI analysis: Change from Baseline WHO-5 up to W16
Treatment Satisfaction Questionnaire for Medication-9 items (TSQM-9)	TSQM-9 up to W16	Primary Estimand (Hybrid)	MMRM and BOCF	FAS	CCI analysis: TSQM-9 up to W16
DLQI-Relevant (DLQI-R)	Change from Baseline DLQI-R up to W16	Primary Estimand (Hybrid)	MMRM and BOCF	FAS	CCI analysis: Change from Baseline DLQI-R up to W16

* The analyses of 4point NRS pruritus improvement will be based on those patients that had a baseline NRS pruritus score \geq 4points

The analyses of 4point DLQI improvement will be based on those patients that had a baseline DLQI score \geq 4points

The analyses of 4point NRS SKIN Pain improvement will be based on those patients that had a baseline NRS SKIN Pain score \geq 4points.

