6.3. Imputation Process for Estimand Handling and Missing Data

Imputation for missing data will occur for primary and key secondary efficacy endpoints.

Where the endpoint is a binary or categorical outcome, the imputation will occur on the binary/categorical outcome.

The following data imputation methods will be employed:

Estimand	Handling Strategy: Imputation
Primary and Key Secondary Efficacy Endpoints	
Main Estimand	
Composite Strategy: Set to baseline (BOCF)Hypothetical Strategy: Set to missing and impute with Markov Chain Monte-Carlo (MCMC) multiple imputation (MI)Missing data not affected by ICE: MCMC MI
Second Estimand: Categorical Endpoints	
Composite Strategy: Set to non-responder (NRI)Missing data not affected by ICE: NRI
Other Secondary and Other Efficacy Endpoints	
Estimand for Categorical Endpoints	
As per main estimand for primary and key secondary efficacy endpoints
Main Estimand for Continuous Endpoints	
As per main estimand for primary and key secondary efficacy endpoints
Second Estimand for Continuous Endpoints	
Hypothetical strategy: Set to missing and do not impute (MMRM)Missing data not affected by ICE: do not impute (MMRM)

Abbreviations: ICE = Intercurrent Event; MCMC = Markov-Chain Monte-Carlo; MI = Multiple Imputation; BOCF, Baseline-Observation-Carried-Forward; NRI = Non-Responder Imputation; MMRM, Mixed Effect Model for Repeated Measures.

Where imputation occurs, imputation will be based on the overall population, and subsequent subgroup analyses (dupilumab naïve and previously exposed to dupilumab) will utilise these imputed data, selecting only the required patients for the analysis.

Where missing data are to be imputed for efficacy using the approaches above, a summary table by week of the frequency and type of missing data will be presented.

General MI Approach ([Section 6.3.1](#)) will be used for

- Main estimand of the primary and key secondary efficacy endpoints
- Main estimand for categorical other secondary efficacy endpoints
- Continuous Other Secondary Efficacy Endpoints

Non-Responder Imputation Approach ([Section 6.3.2](#)) will be used for the Second estimand of the primary and key secondary efficacy endpoints.

This document is confidential.

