6.3.3. Mixed-effects Model for Repeated Measures

Mixed Model for Repeated Measures analyses will be performed on continuous endpoints to mitigate the impact of missing data. This approach assumes missing observations are missing-at-random (missingness is related to observed data) and borrows information from patients in the same treatment arm taking into account both the missingness of data through the correlation of the repeated measurements.

When MMRM is used, the model includes treatment, baseline value, visit, the interaction of the baseline value-by-week, the interaction of treatment-by-week, and the stratification factors mentioned in [Section 7.5](#) as fixed factors.

Example SAS syntax is as follows:

CCI

This document is confidential.

7. General Aspects for Statistical Analysis

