9.3. Analysis of the Primary and Key Secondary Efficacy Endpoints

The primary and key secondary efficacy endpoints (for the main and second estimands) will be analysed by means of a Cochran-Mantel-Haenszel (CMH) model adjusted by country, age (adolescents/adults), prior use of dupilumab (yes/no), and Baseline severity of disease (IGA=3/IGA=4). If the model does not converge, country will be removed as an adjusting factor. The estimate of the adjusted common risk difference, with corresponding Mantel-Haenszel-Sato (Sato 1989) adjusted 2-sided 95% CI and p-value will be presented. Additionally, the CMH adjusted odds ratio along with the 95% two-sided asymptotic CI will be presented. The primary analysis will be based on the FAS which was defined as all randomized patients. When analysing the dupilumab naïve and previously exposed populations, the factor for prior use of dupilumab will be removed from the CMH adjustment.

Details are described in [Appendix 2](#). Details of Combining Estimates and Test Statistics for Categorical Endpoints with Multiple Imputation

Example code for CMH test:

CCI

This document is confidential.

For analyses using multiple imputation, the analysis will be conducted on the complete dataset, for each imputation separately. Modelled results will be combined using Rubin's rule (PROC MIANALYZE).

SAS Proc MIANALYZE will be used to combine the 100 point estimates (main estimand) for the difference in percentage of patients achieving EASI 75 response at Week 16 between treatments and standard errors, allowing appropriate statistical inference as described below:

CCI

The following sensitivity analysis will also be conducted for the main and second estimands of the primary and key secondary efficacy endpoints, on the overall population:

Analysis Set	Modelling Method	Estimand and Data Handling
Sensitivity Analysis Conducted on Main and Second Estimands		
PPS	CMH model adjusted by country, and stratification factors used in the randomisation (age, previous use of dupilumab, and Baseline severity of disease, as per primary analysis).	As per main and second estimands

Abbreviations: CMH = Cochran-Mantel-Haenszel; PPS = Per Protocol Set.

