9.4. Analysis of all Other Secondary and Other Efficacy Endpoint

The main and second estimands as described in Section 6.1.2 will be analysed by means of a mixed effect model for repeated measures (MMRM), including the Baseline value as a covariate, and adjusting by the factors of country, age (adolescents/adults), Baseline severity of disease (IGA=3/IGA=4), previous exposure to dupilumab (yes/no, when the overall population is analysed) and visit and treatment-visit interaction. A restricted maximum likelihood method will be specified, along with an unstructured covariance matrix. Estimates of the LS Means for each of the 2 treatment groups at each visit up to and including Week 16, along with the difference between treatments in LS Means, 2-sided 95% CI and p-value for the difference will be presented.

Example SAS syntax is as follows:

CCI

This document is confidential.

CCI

For all continuous secondary efficacy endpoints, in case of non-convergence, the country factor will be removed from the model.

Time-to-event (TTE) endpoints will be analysed on the second estimand for continuous endpoints using Kaplan-Meier survival analysis methods. If available, for descriptive purposes, the estimate of the median time-to-event (in weeks) and the 2-sided 95% CI will be presented. A comparison of the survival distribution curves for the 2 treatment groups will be made by means of the log-rank test. The Cox proportional hazards model will be used to estimate the hazard ratio and its 95% CI of lebrikizumab compared with placebo at the respective time point. The main Cox proportional hazards model will include treatment group, with country, age, Baseline disease severity and previous exposure to dupilumab (when the overall population is analysed) as factors. The proportional hazard assumption will be evaluated on all factors (ie, treatment and stratification factors) by graphical inspection of the Schoenfeld residuals and by Grambsch and Therneau test as well. Country may be removed from the model as appropriate, similar to the other analyses of efficacy. Because of the fact that the Induction and Maintenance Periods will be reported separately, TTE endpoints will be analysed at 2 separate time points: initially up to and including Week 16, and then separately for the whole study, incorporating both the Induction and Maintenance Periods.

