All binary other secondary and other efficacy endpoints will be analysed using the same methodology as described for the primary efficacy endpoint using only the main estimand. Sensitivity analyses based on the PPS population will not be conducted for these endpoints.

All efficacy variables for the Maintenance/Extension Period will be analysed by means of descriptive statistics presented by treatment group as randomised during the Induction Period.

Additionally, all secondary and CCI efficacy endpoints for the secondary objective will be presented in by-patient listings.

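### The SAP Section 9.6 table assigns MMRM to two responder endpoints (4-point DLQI and 4-point Skin Pain NRS) that the rest of the plan sends to the stratified CMH analysis

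*SAP*

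**What the plan says.** SAP Section 9.6 presents its table as the detailed specification by endpoint, including method and imputation. Two of its rows are responder proportions with the method entry *MMRM and BOCF*: "Proportion of patients achieving at least 4-point improvement in DLQI up to W16" and "Percentage of patients achieving a 4-point improvement Skin Pain NRS at W16". Both are limited to patients with a baseline score of at least 4.

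The text says something else. SAP Section 9.4: "All binary other secondary and other efficacy endpoints will be analysed using the same methodology as described for the primary efficacy endpoint". That rule is confined to the main estimand. Section 6.1.2 says the same, and so does protocol Section 11.8.1.1 B. The primary method in SAP Section 9.3 is a CMH analysis adjusted for country, age group, prior dupilumab and baseline IGA. It reports a common risk difference with a Sato interval, and an odds ratio. Section 6.3 lists "Main estimand for categorical other secondary efficacy endpoints" among the analyses that use the general multiple imputation approach. On MMRM, Section 6.3.3 says: "Mixed Model for Repeated Measures analyses will be performed on continuous endpoints to mitigate the impact of missing data".

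**The concern.** A programmer working from the table would fit a linear mixed model to 0/1 data. One working from Section 9.4 would run CMH. Nothing in the SAP ranks one section above the other. The protocol cannot settle it either, because its Section 11.2 lets the SAP prevail where the two differ. The choice could then be made after the data are unblinded, which pre-specification is meant to prevent.

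The outputs also differ. The MMRM route in Section 9.4 reports LS means and their difference; it gives no Mantel-Haenszel risk difference, Sato interval or odds ratio. Its standard error may differ too. The variance of a binary outcome depends on its response rate, so with 2:1 allocation a single variance for both arms need not match the true one.

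**Working it through.** **1. Is the table entry a deliberate choice?** The table's other binary rows under the main estimand (EASI, IGA and the closely parallel 4-point pruritus row) list MCMC-MI. Only these two responder rows carry the entry used for the continuous rows around them. SAP Section 11, which lists changes from the protocol, mentions no change of method. This reads as a copying slip. The DLQI block may be affected by cell layout, but the skin pain row is unambiguous.

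**2. Inputs.** SAP Section 4.3 gives 208 versus 104 patients, two-sided 5%, and planning rates of 55% v 30% (EASI 75), 30% v 12% (IGA 0/1) and 43% v 9% (4-point pruritus). It gives none for DLQI or skin pain response. As a check on these inputs, the stated power can be reproduced from

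power = Φ{[Δ − 1.96·√(p̄(1−p̄)(1/208+1/104))] / √(p₁(1−p₁)/208 + p₀(1−p₀)/104)}.

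This gives 99.0%, 96.1% and about 100%. The product is 95.2%, in line with the stated figures of more than 95% and more than 90%.

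**3. Standard error of the Week 16 difference.** This takes complete data, one visit and no covariates.

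- Common variance: s² = [208·p₁(1−p₁) + 104·p₀(1−p₀)]/310; SE = √[s²(1/208+1/104)].
- Arm-specific binomial, which the Sato variance approximates: SE = √[p₁(1−p₁)/208 + p₀(1−p₀)/104].

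At 43% v 9%: s² = (208×0.2451 + 104×0.0819)/310 = 0.1919, so the common-variance SE is √(0.1919×0.014423) = 0.0526. The arm-specific SE is √(0.2451/208 + 0.0819/104) = 0.0443. The ratio is 1.19.

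| Rates | Source | Common | Arm-specific | Ratio | Implied 95% CI coverage |
|---|---|---|---|---|---|
| 30 v 30% | assumed (null) | 0.0552 | 0.0550 | 1.00 | 95.1% |
| 55 v 30% | SAP, EASI 75 | 0.0584 | 0.0566 | 1.03 | 95.7% |
| 30 v 12% | SAP, IGA | 0.0504 | 0.0450 | 1.12 | 97.2% |
| 43 v 9% | SAP, pruritus | 0.0526 | 0.0443 | 1.19 | 98.0% |
| 60 v 40% | assumed | 0.0590 | 0.0588 | 1.00 | 95.1% |
| 70 v 50% | assumed | 0.0569 | 0.0584 | 0.975 | 94.4% |
| 80 v 60% | assumed | 0.0521 | 0.0555 | 0.94 | 93.4% |

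Coverage is 2Φ(1.96 × ratio) − 1. With an assumed 146 versus 73 patients left after the baseline restriction, the ratios still run from 0.94 to 1.19.

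**4. Simulation** (6,000 runs per scenario, one binary stratum, complete data). The linear model and the Mantel-Haenszel method gave the same average risk difference. Under equal rates the linear model rejected in 4.8% of runs. Its coverage was 97.6% at 43% v 9% and 93.1% at 80% v 60%. Mantel-Haenszel with the Sato variance stayed between 94.4% and 95.2% throughout.

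**The case against.** The strongest reply is that this is a labelling slip in a table that has others. Nearly every secondary row is called key secondary, and the NRI rows are called hypothetical although Section 6.1.1 calls that estimand composite. The text and protocol agree on the intended method, so a careful statistician would follow them. That supports reading the entry as an error, but it does not remove it from the table that claims to give the detail.

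A reader might go further and infer three things that the documents do not support.

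- *The table drops multiple imputation.* Its method column refers to Section 6.3, where the general imputation approach also covers continuous secondary endpoints. An MMRM entry under the main estimand therefore does not show that imputation is omitted.
- *BOCF is wrong here.* It is the main estimand's composite step for discontinuation for lack of efficacy (ICE2) and for rescue (ICE3). A value set to baseline is a non-response.
- *The analysis is invalid, with wrong standard errors.* The error needs unequal arm variances and one covariance shared by both arms. The visible text says only: "A restricted maximum likelihood method will be specified, along with an unstructured covariance matrix". The SAS code is redacted, so arm-specific covariance cannot be ruled out. The error vanishes under the null and changes sign at high response rates.

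**Conclusion.** The contradiction is real and is in the current text: two binary secondary endpoints carry a method that the SAP describes for continuous ones. The certain consequence is an ambiguous pre-specification and, if the table is followed, the wrong set of reported measures.

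The effect on the standard error is conditional. Assuming a common covariance and complete single-visit data, the ratio to the arm-specific value lies between about 0.94 and 1.19 over the rates tried. It is conservative at the planning rates borrowed from other endpoints and anticonservative at the assumed 70% v 50% and 80% v 60%. Without expected rates for these endpoints, no single figure can be defended.

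The stakes are limited. Neither endpoint is marked as key secondary in protocol Section 6 or SAP Section 3. SAP Section 7.9 makes trial success depend on the primary endpoint alone.

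**What to change.** Before the Induction Period data are unblinded, amend the Section 9.6 table:

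- In the 4-point DLQI and 4-point Skin Pain NRS rows, replace the method entry with CMH analysis with MCMC-MI (BOCF for ICE2 and ICE3).
- Add a row for the 4-point CDLQI response with the same method. It is a listed secondary endpoint with no row of its own.
- Keep MMRM for the continuous CDLQI change from baseline, but correct that row's restricted population (FAS*) and its analysis-type entry, which names the 4-point DLQI response.
- Relabel these rows as secondary, not key secondary.

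The cost is a few table cells and one new row. No data collection or sample size changes.

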9.7. Maintenance Period (and Extension Period for Patients from Germany) Analyses

The Induction and Maintenance/Extension Periods will be reported separately. For the Maintenance/Extension Period, the same analyses as for Induction Period, as described in section エラ
ー! 参照元が見つかりません。, will be performed descriptively on the FAS.

This document is confidential.

10. Safety

The population used for safety analyses will be the Safety Analysis Set (SAF). Safety will be assessed based on adverse event (AE), treatment emergent adverse event (TEAE), vital signs, laboratory results, and physical examinations.

Safety will be described by treatment groups:

- Up to Week 16: Lebri / Placebo
- Up to Week 52/68/Extension period: Lebri-Lebri / Placebo-Lebri

All safety analysis except for laboratory evaluations/vital signs/physical examinations will be summarized for the three study periods described below:

- Induction Period (up to Week 16),
- Maintenance Period and Safety Follow-up:
 - For all patients: from Week 16 to Week 52
 - For all patients except German patients in the extension: from Week 16 to 68
 - For German patients in the extension: from Week 16 to last visit in the German extension
- Combined Induction and Maintenance/Extension Periods (up to Week 52 or later for the Extension as described above – see maintenance period), and Combined Induction and Maintenance/Extension Periods plus Follow-Up Period [selective analysis] (Up to Week 68 or later for the Extension as described above – see maintenance period).

10.1. Adverse Events

Adverse events (AEs) will be coded using MedDRA Version 24.1 or higher. In the event of a missing/incomplete start or stop date associated with an adverse event, only the treatment-emergence will be imputed using the algorithm described in エラー! 参照元が見つかりません。 [section 7.3.2](#). Dates will not be imputed.

A TEAE is any AE that newly appeared, or worsened in severity following initiation of study medication until last follow-up visit. Only TEAE will be included in the summary tables, but all AE will be included in the listings.

Following tables will be produced:

- An overall summary of the number and percentage of patients reporting TEAEs, Adverse Events of Special Interest (AESI), serious TEAEs, Suspected Unexpected Serious Adverse Reactions (SUSARs), TEAEs leading to study drug discontinuation, related TEAEs, related SAEs and Deaths.
- Incidence of AEs (AEs including TEAEs, SAEs, related TEAEs, related SAEs, TEAEs leading to study treatment discontinuation, AESIs and deaths)
- TEAEs overall and by system organ class and preferred term

This document is confidential.

- TEAEs by severity (Mild, Moderate, Severe), overall and by system organ class and preferred term
- TEAEs by relationship to study treatment (unrelated vs. related), overall and by system organ class and preferred term
- TEAEs leading to study drug discontinuation, overall and by system organ class and preferred term
- TEAEs leading to death, overall and by system organ class and preferred term
- Serious Adverse Events, overall and by system organ class and preferred term
- AESIs by severity (Mild, Moderate, Severe), overall and by preferred term
- AESIs by relationship to study treatment (unrelated vs. related), overall and by preferred term
- SUSARs, overall and by system organ class and preferred term

AEs possibly related and related to study medication will be combined for the "related" summaries.

If a patient met the same AE more than one time, AE will be counted only once with the maximum of severity.

